Pulmonary hypertension	A mean pulmonary artery pressure >or equal 25 mm Hg in presence of LAP/wedge <= 15 mm Hg	ACC
Pre-existing condition	A pre-existing condition is one that is present at the start of study treatment. A preexisting condition is not an adverse event unless it worsens as a result of the study treatment.	Sponsor

Term	Definition				Reference/ Justification	
Prosthetic aortic valve stenosis criteria ^a		Normal	Mild	Moderate/severe	VARC-2	
	Quantitative Parameters (flow-dependent)^b					
	Peak velocity (m/s)	<3 m/s	3-4 m/s	>4m/s		
	Mean gradient (mmHg)	<20 mmHg	20-40 mmHg	>40 mmHg		
	Quantitative parameters (flow-independent)					
	Doppler velocity index ^c	>0.35	0.35-0.25	<0.25		
	Effective orifice area ^d	>1.1 cm ²	>1.1-0.8 cm ²	<0.8 cm ²		
	Effective orifice area ^e	>0.9 cm ²	>0.9-0.6 cm ²	<0.6 cm ²		
	^a In conditions of normal or near normal stroke volume (50–70 mL). ^b These parameters are more affected by flow, including concomitant aortic regurgitation. ^c For LVOT >2.5 cm, significant stenosis criteria is <0.20. ^d Use in setting of BSA ≥1.6 cm ² (note: dependent on the size of the valve and the size of the native annulus). ^e Use in setting of BSA <1.6 cm ² .					

Term	Definition				Reference/ Justification
Prosthetic aortic valve regurgitation criteria		Normal	Mild	Moderate/severe	VARC 2
	Semi-quantitative Parameters				
	Diastolic flow reversal in the descending aorta—PW	Absent or brief early diastolic	Intermediate	Prominent, holodiastolic	
	Circumferential extent of prosthetic valve paravalvular regurgitation (%) ^a	<10%	10-29%	≥30%	
	Quantitative parameters^b				
	Regurgitant volume (mL/beat)	<30 mL	30-59 mL	≥60 mL	
	Regurgitant fraction (%)	<30%	30-49%	≥50%	
	EROA (cm ²)	0.10 cm ²	0.10-0.29 cm ²	≥0.30 cm ²	
	
^aNot well-validated and may overestimate the severity compared with the quantitative Doppler.
 
^bFor LVOT >2.5 cm, significant stenosis criteria is <0.20.
				
	Reintervention	
Any intervention that repairs, alters or replaces a previously implanted or operated valve, which occurs after the completion of the valve implant procedure and the transfer to the procedure room. These interventions include:
 
 • Balloon aortic valvuloplasty • Surgical aortic valve replacement • Valve in valve • Paravalvular leak closure 			

Term	Definition	Reference/ Justification
Serious Adverse Event (SAE)	
Adverse Event that:
 
 • Leads to death; • Leads to a serious deterioration in the health of the study patient that: 
 ○ Results in life-threatening illness or injury; ○ Results in a permanent impairment of a body structure or a body function; ○ Requires inpatient hospitalization or prolongation of existing hospitalization; ○ Results in medical or surgical intervention to prevent permanent impairment to body structure or a body function; • Led to fetal distress, fetal death or congenital abnormality or birth defect; • Significant medical event 
Important medical events that do not meet the above criteria may still be considered an SAE if they seriously jeopardize the patient and require immediate medical or surgical intervention to prevent one of the aforementioned outcomes.
	ISO 14155-1:2011 FDA (21 CFR 312.32 (a))
Sternal wound dehiscence	Opening of sternal with negative cultures and no signs of infection requiring a procedure or operation for treatment	Sponsor
Valve implant procedure	
Placement of study device and/or additional procedures occurring in the cath lab and/or operating room which are completed prior to subject transfer to a post-procedure recovery unit (e.g. Recovery Room, ICU/CCU, etc.
 
The valve implant procedure will be considered to have started when:
 
 • The first interventional access related puncture (venous or arterial) is established for TAVR. • The first skin incision is performed for SAVR. 
Performance of TEE does not by itself constitute start of procedure
	Sponsor
Valve Thrombosis	Valve thrombosis is any thrombus not caused by infection attached to or near an operated valve that occludes part of the blood flow path, interferes with valve function, or is sufficiently large to warrant treatment.	VARC2
Stroke / Transient Ischemic Attack	Diagnostic Criteria	VARC 2

Term	Definition	Reference/ Justification
(TIA)	
Acute episode of a focal or global neurological deficit with at least one of the following:
 
  change in level of consciousness  hemiplegia  hemiparesis  numbness or sensory loss affecting one side of the body  dysphasia or aphasia  hemianopia  amaurosis fugax  or other neurological signs or symptoms consistent with stroke 
Duration of a focal or global neurological deficit >24 h; OR <24 h, if available neuroimaging documents a new hemorrhage or infarct; OR the neurological deficit results in death
 
No other readily identifiable nonstroke cause for the clinical presentation (e.g., brain tumor, trauma, infection, hypoglycemia, peripheral lesion, pharmacological influences) to be determined by or in conjunction with designated neurologist*
 
Confirmation of the diagnosis by at least one of the following#:
 
  Neurology or neurosurgical specialist  Neuroimaging procedure (MR or CT scan)  Clinical presentation alone 
Stroke definitions†:
 
  Non-disabling: a mRS score of less than 2 at 90 days or the last available clinical visit with evaluable data or one that does not result in an increase of at least one mRS category from an individual's pre-stroke baseline  Disabling: a mRS score of 2 or more at 90 days or the last available clinical visit with evaluable data and an increase of at least one mRS category from an individual's pre-stroke baseline 
Stroke classification:
 
  Hemorrhagic: an acute episode of focal or global cerebral or spinal dysfunction caused by intraparenchymal, intraventricular, or subarachnoid hemorrhage. 	

Term	Definition	Reference/ Justification
	
□ Ischemic: an acute symptomatic episode of focal cerebral, spinal, or retinal dysfunction caused by an infarction of the central nervous system tissue
 
□ Undetermined: stroke with insufficient information to allow categorization as ischemic or hemorrhagic.
 
Transient Ischemic Attack (TIA)
 
Duration of focal or global neurological deficit <24 h, any variable neuroimaging does not demonstrate a new hemorrhage or infarct
 
*Patients with non-focal global encephalopathy will not be reported as a stroke without unequivocal evidence based upon neuroimaging studies.
 
#If a stroke is reported without evidence of confirmation of the diagnosis by one of these methods, the event may still be considered a stroke on the basis of the clinical presentation alone.
 
†Modified Rankin score assessments should be made by qualified individuals according to a certification process.
	
Structural performance	Evaluation of migration, embolization, fracture, or thrombosis	FDA
Structural Valvular Deterioration (SVD)	Structural valve deterioration includes dysfunction or deterioration exclusive of infection or thrombosis as determined by reoperation, autopsy or clinical investigation. The term structural deterioration refers to changes intrinsic to the valve, such as wear, fracture, calcification, leaflet tear, leaflet retraction, suture line disruption of components a prothetic valve, thickening, stenosis	Akins, Cary W., et al. "Guidelines for reporting mortality and morbidity after cardiac valve interventions." European Journal of Cardio-Thoracic Surgery 33.4 (2008): 523-528.
STS Adult Cardiac Surgery Risk Calculator	The Society of Thoracic Surgeons' risk models predict the risk of operative mortality and morbidity after adult cardiac surgery on the basis of patient demographic and clinical variables. http://riskcalc.sts.org/stswebriskcalc/#/	STS
Syncope	A fainting spell or loss of consciousness	STS
SYNTAX Score	An angiographic grading tool to determine the complexity of coronary artery disease. http://www.syntaxscore.com/ http://ir-nwr.ru/calculators/syntaxscore/frameset.htm	

Term	Definition	Reference/ Justification
6 Minute Walk Test	A performance-based measure of functional exercise capacity. The test measures the distance an individual is able to walk over a total of six minutes on a hard, flat surface. See more at: http://www.rheumatology.org/I-Am-A/Rheumatologist/Research/Clinician-Researchers/Six-Minute-Walk-Test-SMWT#sthash.cFCDWfkn.dpuf	ATS
THV-in-THV	An additional valve prosthesis is implanted within a previously implanted prosthesis because of suboptimal device position and/or function, during or after the valve implant procedure	VARC 2
Transient Ischemic Attack (TIA)	See “Stroke / Transient Ischemic Attack (TIA)”	
Unanticipated Adverse Device Effect (UADE)	Any serious adverse effect on health or safety or any life-threatening problem or death caused by, or associated with, a device, if that effect, problem, or death was not previously identified in nature, severity, or degree of incidence in the investigational plan or application (including a supplementary plan or application), or any other unanticipated serious problems associated with a device that relates to the rights, safety, or welfare of patients.	FDA
Vascular injury	Injury that may be caused by a guidewire, vascular sheath, delivery catheter, or any balloon used for aortic valve predilatation and can include arterial dissection, perforation, arteriovenous fistula, pseudoaneurysm formation, retroperitoneal hemorrhage, or incomplete arteriotomy closure. Venous injuries can include perforation, tears and thromboembolism. Cardiac vascular injury can include perforation or tearing of the major cardiac structures that require repair.	Sponsor
Valve malpositioning	
Valve migration
 
 • After initial correct positioning, the valve prosthesis moves upward or downward, within the aortic annulus from its initial position, with or without consequences 
Valve embolization
 
 • The valve prosthesis moves during or after deployment such that it loses contact with the aortic annulus 
Ectopic valve deployment
 
 • Permanent deployment of the valve prosthesis in a location other than the aortic root 	VARC 2

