8.4 Post Procedure

The post implant procedure time period is defined as the 48 hours after the patient exits the cath lab/ operating room. Study patients will be continuously monitored clinically, hemodynamically, and electrocardiographically during catheterization for all local, systemic side effects and complications. After completion of the implant procedure, all study patients will be monitored per institution standard of care. Subsequent monitoring will also be continued according to institutional standard of care.

The following information will be collected during the Post Procedure time period:

Systems:

- Medications including all antithrombotics/anticoagulants and HMG coA reductase inhibitors .
- Adverse event assessment

Cardiopulmonary:

- 12-lead ECG

Clinical Laboratory Tests:

- WBC, Hgb, and platelet count
- PT or INR
- CK/CKMB and/or Troponins will be performed to monitor the patient's cardiac enzymes at 3 different time intervals. Of note, patients discharged prior to the completion of 24 hour series of lab tests will not be issued deviations.
 - The first lab draw post implant procedure (within 8 hours of exit from the cath lab / operating room)
 - The second lab draw, (6 – 8 hours after the first lab draw)
 - The third lab draw, (6 – 8 hours after the second lab draw)
- Creatinine

Neurological assessments:

- NIHSS

All patients should be assessed post-procedure to determine if there is evidence of neurological impairment. If symptoms of stroke are suspected, the NIHSS should be performed. For all patients diagnosed with stroke after procedure, a follow-up mRS assessment 90 days after the diagnosis should be performed (on site or phone calls). Evaluation of stroke by mRS between 30 and 90 days is acceptable if 90-day follow-up not available. Every effort should be made to have a neurologist (or neurology fellow) perform the assessment. If it is not possible to have the neurologist/fellow complete this within the protocol-specified visit window, a certified study team member may perform the assessments.

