8.5 Discharge

Discharge is the actual date and time the patient is discharged. For patients discharged within 48 hours of exiting the cath lab / operating room, it is not required to repeat tests collected during the Post Procedure period that are also required for the discharge visit. If the patient was discharged over a weekend or holiday, the discharge assessments may be completed on the last weekday prior to discharge.

The following information will be collected for study patients within 24 hours of the date and time of discharge.

Systems:

- Physical assessment including weight, blood pressure, and heart rate
- Medications including all antithrombotics/anticoagulants and HMG coA reductase inhibitors.
- Adverse event assessment

Cardiopulmonary:

- NYHA classification
- Comprehensive transthoracic echocardiogram (TTE)

Clinical Laboratory Tests:

- WBC, Hgb, and platelet count
- PT or INR
- Creatinine
- BNP

Neurological Assessments:

- NIHSS

All patients should be assessed at Discharge to determine if there is evidence of neurological impairment. If symptoms of stroke are suspected, the NIHSS should be performed. For all patients diagnosed with stroke after procedure, a follow-up mRS assessment 90 days after the diagnosis should be performed (on site or phone calls). Evaluation of stroke by mRS between 30 and 90 days is acceptable if 90-day follow-up not available. Every effort should be made to have a neurologist (or neurology fellow) perform the assessment. If it is not possible to have the neurologist/fellow complete this within the protocol-specified visit window, a certified study team member may perform the assessments.

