11.6 Additional Safety and Effectiveness Endpoints

The endpoints in this section will be evaluated according to the general statistical methods described in section 11.8. These endpoints will not be subject to the formal multiple comparisons correction; they are presented as part of the totality of information. All the statistical tests between the treatment arms will be two-sided tests at $\alpha=0.05$.

- Mortality (all cause & cardiovascular) at 30 days and 1 year
- Stroke (disabling and nondisabling) at 30 days and 1 year
- Death or stroke at 1 year
- Death or disabling stroke at 30 days and 1 year
- Vascular complications (major) at 30 days and 1 year
- Bleeding complications (life threatening, disabling or major) at 30 days and 1 year
- Myocardial infarction at 30 days and 1 year
- Acute kidney injury at 30 days
- Requirement for renal replacement therapy at 1 year
- New permanent pacemaker implantation resulting from new or worsened conduction disturbances at 30 days and 1 year.
- Coronary obstruction requiring intervention at 30 days and 1 year

- New York Heart Association class at 30 days and 1 year
- Hemodynamic valve performance evaluation by echocardiography for aortic valve stenosis and aortic valve regurgitation at 30 days and years 1, 2, 3, 4, 5, 7, and 10. Echo readings to be evaluated include aortic valve area, mean gradient, peak gradient, perivalvular aortic regurgitation, total aortic regurgitation, and mitral regurgitation.
- Rehospitalization (valve-related or procedure-related and including heart failure) at 30 days, 1 year and annually (up to 10 years)
- Days alive and out of hospital at 1 year
- Six-minute walk test at 30 days and 1 year
- Health status as evaluated by Quality of Life questionnaires at 30 days and 1 year
- New onset atrial fibrillation at 1 year
- ICU days and discharge location
- Structural valve deterioration at years 1-5,7 and 10

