Appendix B Definitions

Term	Definition	Reference/ Justification
Adverse Event (AE)	Any untoward medical occurrence, unintended disease or injury, or untoward clinical signs (including abnormal laboratory findings) in subjects, users or other persons, whether or not related to the investigational medical device	ISO 14155-1:2011 GCP
Access Site	Any location (arterial or venous) traversed by a guide-wire, a catheter or a sheath for TAVR or skin incision for SAVR	VARC 1
Access site related complication	Any adverse clinical consequence possibly associated with any of the access sites used during the procedure	VARC 1
Acute kidney injury	
An abrupt loss of kidney function, resulting in the retention of urea and other nitrogenous waste products
 
The increase in creatinine meeting at least Stage 1 must occur within 48 hours. Staging will be based on the worse stage that occurs within 7 days of the index procedure.
 
Stage 1
 
 Increase in serum creatinine to 150-199% (1.5-1.99 × increase compared with baseline) OR increase of ≥0.3 mg/dL (≥26.4 mmol/L) OR Urine output <0.5 ml/kg per hour for >6 but <12 hours 
Stage 2
 
 Increase in serum creatinine to 200-299% (2.0-2.99 × increase compared with baseline) OR Urine output <0.5 ml/kg per hour for >12 but <24 hours 
Stage 3
 
 Increase in serum creatinine to ≥300% (>3 × increase compared with baseline) OR serum creatinine of ≥4.0 mg/dL (≥354 mmol/L) with an acute increase of at least 0.5 mg/dL (44 mmol/L) OR Urine output <0.3 ml/kg per hour for ≥24 hours OR Anuria for ≥12 hours 
Patients receiving renal replacement therapy (dialysis, hemodialysis, peritoneal dialysis, hemofiltration, transplant) are considered to meet Stage 3 criteria irrespective of other criteria irrespective
	Sponsor/VARC 2
Anemia	A condition in which the blood is deficient in red blood cells, in hemoglobin, or in total volume, without clear evidence of overt bleeding, that is actionable (e.g. requires medications, transfusion etc)	Sponsor

Term	Definition		Reference/ Justification
Angina / Cardiac chest pain	Chest pain due to an inadequate supply of oxygen to the heart muscle		Sponsor
Angina, grading scale	Grade	Description	Canadian Cardiovascular Society

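### AKI ascertainment depends on length of stay, so the between-arm AKI comparison may favour the shorter-stay arm (plausibly TAVR) by an unknown and probably small amount

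*Combined protocol and SAP*

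**What the plan says.** **Definition (Appendix B, Acute kidney injury).** On onset: "The increase in creatinine meeting at least Stage 1 must occur within 48 hours". On severity: "Staging will be based on the worse stage that occurs within 7 days of the index procedure". The 48 hours has no stated starting point. Every stage has a urine-output alternative; for Stage 1 it is "Urine output <0.5 ml/kg per hour for >6 but <12 hours". Renal replacement therapy counts as Stage 3 whatever the other criteria show.

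**Sampling (sections 8.1 and 8.4 to 8.6, Schedule of Procedures).** Creatinine is listed at four points:
- Screening, within 30 days before the procedure.
- Post-procedure, once and without a clock time. The window is broad: "The post implant procedure time period is defined as the 48 hours after the patient exits the cath lab/ operating room".
- Discharge: "The following information will be collected for study patients within 24 hours of the date and time of discharge". For patients who leave within 48 hours of room exit, however, "it is not required to repeat tests collected during the Post Procedure period that are also required for the discharge visit".
- The 30-day visit (+7 days).

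Urine output is not an item at any visit. By contrast, section 8.4 does time the cardiac enzymes: "CK/CKMB and/or Troponins will be performed to monitor the patient's cardiac enzymes at 3 different time intervals".

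**Analysis (section 11.6).** "Acute kidney injury at 30 days" is an additional endpoint, compared two-sided at 0.05 with no multiplicity correction. No qualifying stage is named.

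**The concern.** The definition relies on serial creatinine over two days and worst values over seven. The schedule guarantees much less. A patient who goes home within 48 hours can have a single scheduled value, perhaps a few hours after the procedure, and nothing more until the staging window has long closed. A patient who stays three to seven days has a second value inside that window. The urine-output route can be met only where hourly output happens to be charted, which the protocol leaves to local practice.

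If stay differs by arm, the chance of finding the same true AKI differs by arm too. There are signs that it will. Section 11.5 puts length of index hospitalization second in the labeling sequence. Section 8.4 excuses patients discharged before the 24-hour enzyme series is complete. The bleeding definition in Appendix B uses an intake-and-output chart for SAVR but procedural blood loss for transfemoral TAVR, which suggests, without proving, that fluid charting will be fuller after surgery. At stake is a published two-arm AKI comparison that could partly reflect how often creatinine was measured.

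**Working it through.** The plan states no AKI power calculation or arm-specific rate, so there is no figure of its own to reproduce. The check has three parts.

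**1. Scheduled creatinine draws by length of stay** (hours from room exit, waiver used, draw times uniform within their windows)

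| Stay | Draws in first 48 h | Draws in 7 days |
|---|---|---|
| Up to 48 h | 1 | 1 |
| 60 h | 1.5 on average | 2 |
| 72 to 168 h | 1 | 2 |
| 8 days or more | 1 | 1 (discharge draw falls after day 7) |

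**2. Illustrative detection.** Assume the rise crosses threshold at a time uniform over 6 to 48 h and lasts 48 to 144 h. For a stay of L hours, L ≤ 48, with one draw uniform over 0 to L:

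P(detect) = (1/L) ∫ from 6 to L of (d − 6)/42 dd = (L − 6)² / (84 L)

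- L = 24: 18²/2016 = 0.16
- L = 36: 30²/3024 = 0.30
- L = 48: 42²/4032 = 0.44

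Longer stays depend on how the 48-hour limit is read (simulated under the same assumptions):
- Rise must be seen within 48 h of the procedure: 0.65 at 60 h, then 0.44 for 72 to 168 h, the same as a 48 h stay.
- Any value to day 7 may establish the rise: 0.44 to 1.00 across stays of 60 to 168 h, depending on how long the rise lasts.

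Stays well under 48 h are under-sampled on both readings. Beyond that, the ordering depends on the reading. The levels also depend on the onset assumption: with onset uniform over 12 to 48 h, a draw uniform over 0 to 24 h detects 12²/(2 × 36 × 24) = 0.08, and one over 0 to 48 h detects 36²/(2 × 36 × 48) = 0.38.

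**3. What unequal detection would do.** Take equal true rates p, full detection in SAVR, detection s in TAVR, and 500 per arm (half of the 1000 in section 11.1). The spurious difference is p(s − 1). The last two columns give the chance of a two-sided p < 0.05 favouring TAVR.

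| True AKI rate | Difference, s = 0.9 to 0.5 (points) | Normal approximation | Fisher's exact |
|---|---|---|---|
| 0.5% | −0.05 to −0.25 | 3 to 10% | 0.5 to 1.3% |
| 2% | −0.2 to −1.0 | 4 to 26% | 3 to 18% |
| 5% | −0.5 to −2.5 | 6 to 55% | 4 to 49% |
| 10% | −1 to −5 | 8 to 85% | 6 to 83% |

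With equal detection the normal-approximation chance is 2.5%. At a true rate of 0.5% there are only 500 × 0.005 = 2.5 expected events per arm, so the exact column is the one to read there.

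The only AKI rate in the documents is the 30-day figure in section 1.2.2 for the single-arm, intermediate-risk SAPIEN 3 cohort: 0.5% overall and 0.3% transfemoral. The stage is not stated and there is no SAVR rate.

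**The case against.** A reader might infer that the comparison is biased toward TAVR as a matter of fact. The documents do not support that.

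- **No expected stay is given for either arm.** Shorter TAVR stay is a hypothesis tested in section 11.5. The direction is an inference from the plan's design, not a stated premise.
- **The 48-hour limit may remove much of the asymmetry.** If it runs from the procedure, most longer-stay SAVR patients also have one scheduled draw that can establish onset, and a stay of 8 days or more loses its discharge value from the 7-day window.
- **Scheduled draws are not the only data.** Section 8.4 leaves monitoring to institutional standard of care. Section 9.5 makes all adverse events reportable for 12 months, with laboratory results among the supporting documents for endpoint-related events. The CEC adjudicates endpoint events, and section 11.8.7 prefers its result.
- **An ageing screening creatinine does not bias the arms.** Screening precedes randomization, so its error is the same in both.

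All four stand as limits on direction and size. The third does not close the gap. Adjudication cannot recover a creatinine that was never drawn. Section 9.5 also exempts non-significant laboratory variances from reporting, so a small qualifying rise may never reach the CEC. Routine draws are uncontrolled and may themselves follow length of stay.

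**Conclusion.** The schedule, followed as written, makes AKI ascertainment depend on length of stay. Confidence in that is high. Confidence that it favours TAVR is moderate, because it rests on TAVR stays being shorter and on how the 48 hours is read.

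The size is unknown. It is probably small if AKI in both arms is as rare as the 0.5% in section 1.2.2, where even a halving of detection moves the difference by 0.25 points. It would matter at true rates of several percent, which the documents neither give nor exclude for SAVR. The detection probabilities above are illustrations under assumed onset and draw times, not estimates.

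AKI is one of 20 additional endpoints. The primary non-inferiority test and the labeling sequence do not use it. Severity is minor, but the remedy is cheap enough to be worth making.

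**What to change.** 1. **Common draw time.** Take the required post-procedure creatinine with the third enzyme draw in both arms, or immediately before discharge if the patient leaves earlier. From section 8.4, the first draw is within 8 h of room exit and each later draw follows by 6 to 8 h, so the third falls between 0 + 6 + 6 = 12 h and 8 + 8 + 8 = 24 h. Add a sensitivity comparison of the arms using only creatinine in that window plus renal replacement.
2. **Baseline.** Add creatinine to the CK/troponin sample already required within 72 hours before the procedure. This improves precision and is not an arm-bias correction.
3. **Definition.** State whether the 48-hour limit runs from the procedure. Keep the protocol definition as the main analysis, with any later values from routine care still counted, and report AKI met on urine output alone separately.

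**Cost.** Wording in Appendix B, section 8.4, the schedule footnotes and the analysis section; creatinine is added to blood already being drawn. The common-window analysis misses later-onset AKI: in the model above, a draw uniform over 12 to 24 h (mean 18 h) detects (18 − 6)/42 = 0.29, equal across arms but below the 0.44 of an untimed draw in a 48 h stay. Some very short-stay patients may lack the third draw, since its omission after early discharge is not a deviation; for them a pre-discharge value still varies with stay. Report how many there are in each arm.
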